14.0 Risks to Subjects

14.1 Physical, psychological, social, cultural, financial, and legal risks, and risks to privacy and/or confidentiality associated with this research are minimal because the probability and magnitude of harm or discomfort anticipated in the proposed research are not greater, in and of themselves, than those ordinarily encountered in daily lives of the general population or during the performance of routine physical or psychological examinations or tests.

These minimal risks include:

1. Possible breach of participant privacy and/or confidentiality
2. Possible breach of the security of participant online data
3. Possible participant discomfort due to completing psychological questionnaires and assessments
4. Possible participant discomfort due to having therapy sessions recorded
5. Participant discomfort during exposure therapy exercises. This discomfort is temporary but necessary for treatment gains to occur.
6. Possible participant discomfort or cybersickness as a result of using the VR system, the duration of which is typically 5-10 minutes, and which will be assessed following each VR-based exposure using the CSQ-VR.
7. Possible disclosure of suicidality or homicidality requiring mandatory reporting if participants are at imminent risk of endangering themselves or others. Standard operational procedures of the USF Department of Psychiatry and Behavioral Neurosciences specify responsibilities for handling dangers to self and others, safety planning, and mandatory reporting responsibilities.

14.2 N/A

14.3 N/A

15.0 Potential Benefits to Subjects or Others

15.1 Potential direct benefits to participants include reductions in anxiety associated with feared stimuli.

15.2 The general public and scientific community will benefit from the knowledge produced in this research. This includes preliminary knowledge about the comparative efficacy of a telemedicine-based VR clinic vs. Standard TMH in the treatment of specific phobias.

16.0 Data Management and Confidentiality

16.1 We will assess feasibility of the proposed trial methodology using the following benchmarks: 30 participants will be enrolled in months 1-9 of trial, 70% of participants will be retained at three-month follow-up, 70% of weekly self-report assessments will be completed, and we will reach 80% or greater treatment fidelity.

The small sample size prevents any conclusions about efficacy; however, Analysis of Covariance will be used to conduct a preliminary assessment of between-group differences in clinical outcomes while co-varying for pre-treatment scores. We also will conduct a preliminary examination of associations between study targets including therapeutic alliance and presence.

16.2 D.

We will use the following security measures to protect data sources:

1. Data collected during the trial will be securely stored in a HIPAA compliant USF REDCap database, including informed consent documents, questionnaire data, and session notes.
2. Consent forms and de-identified data will be downloaded and stored in a secure HIPAA compliant Box folder.
3. All research data exported from REDCap will include ID numbers only.
4. Audio recordings will be stored in a secure HIPAA compliant USF Box folder.
5. Only IRB-approved and trained study personnel will have access to the REDCap project and box folder.
6. Computers, programs, and box folders containing data will be password-protected to prohibit unauthorized access.
7. The codes that link the name of the participant and the study ID will be kept confidential in REDCap along with other identifiers including first name, last name, full date of birth, address, email address, and cell phone number.
8. We have obtained a Certificate of Confidentiality from the National Institutes of Health so that we cannot be forced to disclose information that may identify participants, even by a court subpoena, in any federal, state, or local civil, criminal, administrative, legislative, or other proceedings.

16.3 We will use the following quality assurance measures for subject recruitment, enrollment, enrollment targets, and for the validity and integrity of the data:

1. study staff will complete and maintain up-to-date CITI and GCP training

2. study staff will be trained and supervised weekly by the PI
3. Standard Operating Procedures (SOPs) and study checklists will be used to train study staff and ensure fidelity to the study protocol
4. informed consent will be obtained and documented by study staff to provide an audit trail
9. any contact with study participants or potential study participants will be documented to provide an audit trail
10. participant screening, recruitment, enrollment and enrollment targets, and data collection will be tracked to provide weekly updates to the PI
11. assessment data will be entered directly by participants into REDCap
12. automated validity checks will be in place for any data collection
13. data checks for ranges, cross-validity, and completion will be completed proximal to data collection
14. collection of any study data will be documented by study staff to provide an audit trail
15. the USF Conflict of Interest (COI) Office will maintain and monitor study progress according to ongoing conflict of interest management plans to ensure compliance with all requirements

16.4 Identifiable information in this study will include patient names, dates of birth, phone numbers, email addresses, and physical addresses. Analyzed data will not include participant's identifiable information and will only be shared with the public in aggregate form. Human subjects research records, including the original signed and dated consent documents, will be stored for at least 5 years after study completion. Signed and dated HIPAA authorizations and consent documents that include HIPAA authorizations will be stored for at least 5 years after study completion. After this time data will be deleted from REDCap. Patient assessment results and session notes will be shared with their healthcare provider upon submission of a signed release of information form, as stated in the informed consent document.

16.5 If you will review/access and/or collect/obtain Protected Health Information (PHI) during recruitment or the main study, select all that apply:

 Obtaining Signed Authorization	 Waiver of HIPAA Authorization for Recruitment/Screening Purposes Only
 Obtaining Online or Verbal Authorization (Alteration of HIPAA Authorization)	 Waiver of HIPAA Authorization for Entire Study
 Data Use Agreement	 Business Associate Agreement

No Protected Health Information will be obtained during recruitment or the main study. As stated above, all identifiable information will be provided by the participant within the context of the study. No medical or insurance records will be accessed.

16.6 Members of this research team are dedicated to the timely dissemination of study products and results. This includes the data used to inform Doxy.me VR features and

exercises and resulting publications from analyses. We will prepare both brief and comprehensive reports for NIH, which will be circulated for review and comment to our colleagues in the field and the NIH. We will provide relevant information to senior leaders, supervisors, and providers at community health clinics and academic clinics located locally, regionally, and nationally. Results will be shared via professional, peer-review, and lay publications, as well as presentations and forums, websites, newsletters, among others.

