2.0 Objectives

2.1 Primary Objective: Assess the feasibility of conducting a randomized controlled efficacy trial comparing the delivery of exposure therapy via a telemedicine-based virtual reality clinic (Doxy.me VR) vs. standard telemental health (TMH) to adults with intense fear of dogs, snakes, and/or spiders.

Secondary Objective: Preliminarily examine the efficacy of using Doxy.me VR vs. TMH in reducing phobia severity.

2.2 This is a feasibility trial and not powered for hypothesis testing.

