5.0 Procedures Involved

This study will use feasibility randomized controlled efficacy trial design. This single-site trial will include up to 60 adults with self-reported fear of dogs, snakes, and/or spiders who will be randomly assigned via the REDCap Randomization Module using a 1:1 allocation ratio to receive 12 sessions of exposure therapy over the course of 3 months via standard telemental health (TMH; $n=15$) vs. Doxy.me VR ($n=15$), a telemedicine-based virtual reality clinic. Participants randomized to the Doxy.me group will be provided with Quest 2 VR headsets with the Doxy.me VR application pre-loaded to the device. This VR clinic is a standalone app currently available on Quest 2 headsets via

invite only. The app is designed for a therapist to meet with a client in a private, comfortable VR clinic office. To join each other in VR, the therapist selects a room code and provides that code to their client, who joins by entering that code into the app. While in the same VR room, the therapist and client can interact by speaking with each other in immersive VR. Therapists can also spawn a variety of small animals such as dogs, snakes, and spiders for use in treating specific phobias. Therapists can browse, select, maneuver, remove, and choose animations for the animals to exhibit once made visible to the client.

Therapy sessions will be audio recorded and 20% will be observed by the PI to assess treatment fidelity. Primary clinical outcomes (i.e., phobia severity as measured by the SMSF) will be assessed at baseline and 3-months post-baseline. Intervention targets will include presence—assessed weekly via patient-report— and working alliance—assessed at mid- and post-treatment via study therapist- and patient-report. Benchmarks for feasibility will include enrolling up to 60 patients during months 1-9 of the trial (i.e., 3/month), 70% patient retention at 3-month follow-up, 70% of weekly self-report collected, and $\geq 80\%$ treatment fidelity.

5.2 Please select the methods that will be employed in this study (select all that apply):

 Audio/Video Recording	 Psychophysiological Recording
 Behavioral Interventions	 Record Review - Educational
 Behavioral Observations and Experimentations	 Record Review - Employee

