9.4 N/A

10.0 Vulnerable Populations

10.1 N/A

11.0 Local Number of Subjects

11.1 We aim to complete treatment with and obtain post-treatment assessment data from a total of 30 participants (15 in TMH and 15 in VR group). We will enroll up to 60 participants in the trial as needed to account for screen fails, withdrawals, and drops.

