12.3 N/A

13.0 Withdrawal of Subjects

13.1 Anticipated circumstances under which participants will be withdrawn from the research without their consent include the event that they:

1. Begin participating in ongoing mental health therapy from a non-study therapist
2. Have changes to psychotropic medication use
3. Begin to report active suicidal and/or homicidal intent or plan
4. Begin to report active auditory, visual, and/or tactile hallucinations
5. Begin to report the occurrence of photosensitive epilepsy or seizures
6. Moves out of the State of Florida during the study period

13.2 If subjects completely withdraw from the research, study staff will attempt to provide them with a referral to a therapist in their area. If subjects partially withdraw from the research, study staff will attempt to administer mid- and post-treatment assessments. Subjects will be given the option to completely withdraw from the study including withdrawing previously collected data.

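### The retention, weekly-report and fidelity benchmarks name no arm, so 70% can be met with VR at 40%, and what the 70% is taken of is unclear

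*Protocol*

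**What the plan says.** The primary objective (Protocol 2.1) is to "Assess the feasibility of conducting a randomized controlled efficacy trial comparing the delivery of exposure therapy" by VR clinic or by standard telemental health. Allocation is 1:1 (5.0).

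The criteria for that objective appear twice.

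- Section 16.1: "30 participants will be enrolled in months 1-9 of trial", then "70% of participants will be retained at three-month follow-up, 70% of weekly self-report assessments will be completed", and finally "we will reach 80% or greater treatment fidelity".
- Section 5.0: "Benchmarks for feasibility will include enrolling up to 60 patients during months 1-9 of the trial (i.e., 3/month), 70% patient retention at 3-month follow-up", followed by the same weekly-report and fidelity thresholds.

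Neither section names an arm or says which participants form the base of the 70%. Where the protocol wants figures by arm it gives them: section 11.1 aims to "obtain post-treatment assessment data from a total of 30 participants (15 in TMH and 15 in VR group", and allows enrolment of up to 60 to cover screen failures, withdrawals and dropouts. That is a target for completers, not a feasibility benchmark.

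Section 13.2 has staff attempt mid- and post-treatment assessments after a partial withdrawal. On complete withdrawal, it states: "Subjects will be given the option to completely withdraw from the study including withdrawing previously collected data".

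**The concern.** The two arms do not carry the same delivery burden. Only VR participants are mailed a headset, must return it, and move into the VR clinic for exposures (section 5.0, Treatment). Cybersickness is a listed risk of the VR system (14.1). Uneven loss between arms is therefore a foreseeable way for this comparison to prove infeasible, and a single trial-level percentage cannot show it. Good retention on TMH can offset poor retention on VR.

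A larger trial planned from such a result could inherit differential attrition, which would weaken its efficacy comparison. If the base of the percentage is also open, the same data could be read as meeting or missing the benchmark.

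**Working it through.** **Inputs.** From the protocol: thresholds of 70%, 70% and 80% (5.0, 16.1); 1:1 allocation and 15 per arm (5.0); 30 completers and up to 60 enrolled (11.1); 3 per month over nine months (5.0). The 70% is a chosen threshold with no derivation, so there is no calculation of the plan's to reproduce. All true retention rates below are assumptions.

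**1. Lowest VR figure compatible with meeting the benchmark**

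- Retention, N = 30: 0.70 × 30 = 21 needed. With TMH at 15/15, VR needs 21 − 15 = 6, and 6/15 = 40%.
- Retention, N = 60: 0.70 × 60 = 42 needed. With TMH at 30/30, VR needs 12, and 12/30 = 40%.
- Weekly reports, assuming 12 forms per person (one per therapy session) and N = 30: 0.70 × 360 = 252 needed. With TMH at 180/180, VR needs 72, and 72/180 = 40%.
- Fidelity, assuming equal numbers of rated sessions per arm and an averaged score: with TMH at 100%, VR can be 2 × 80 − 100 = 60%.

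**2. How often an overall pass would hide a low VR arm**

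Let T ~ Bin(15, p_T) and V ~ Bin(15, p_V) be the numbers retained. The overall benchmark is met if T + V ≥ 21. An arm reaches 70% at 11/15, since 0.70 × 15 = 10.5.

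| Assumed TMH / VR | P(T+V ≥ 21) | P(V ≥ 11) | P(T+V ≥ 21 and V ≤ 10) |
|---|---|---|---|
| 90% / 50% | 0.59 | 0.06 | 0.53 |
| 85% / 55% | 0.59 | 0.12 | 0.47 |
| 90% / 60% | 0.82 | 0.22 | 0.60 |
| 80% / 60% | 0.59 | 0.22 | 0.38 |
| 80% / 80% | 0.94 | 0.84 | 0.12 |

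In the first four rows the overall benchmark is more likely than not to be met, although true VR retention is 50% to 60%.

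**3. What a hard rule of 70% in each arm would cost**

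P(T ≥ 11) × P(V ≥ 11), against the overall rule:

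- 80% / 80%: 0.70 against 0.94.
- 75% / 75%: 0.47 against 0.80.
- 90% / 90%: 0.975 against about 1.00.

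Exact 95% confidence intervals: 21/30 gives 51% to 85%; 11/15 gives 45% to 92%; 6/15 gives 16% to 68%.

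**4. What the 70% is taken of**

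- Section 16.1: 30 enrolled in nine months, which needs 30/9 = 3.33 per month.
- Section 5.0: up to 60 in nine months, which needs 60/9 = 6.67 per month. The stated 3 per month gives 3 × 9 = 27, matching neither 30 nor 60.
- Section 11.1: 30 completers. At 70% retention this implies 30/0.70 = 42.9, so 43 randomised. If all 60 were randomised to obtain them, retention would be 30/60 = 50%, below the benchmark.

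**The case against.** The strongest reply is that pooling is inferred from silence. Neither section uses the word or excludes results by arm, and tabulation by arm is commonly left to an analysis plan, which is not shown here. That stands as to wording. But these are the criteria for the primary objective, the protocol itself fixes them, and a percentage of participants with no arm named reads naturally as everyone together.

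Second, the 40% case is extreme. At 85% / 55%, exactly 15/15 with 6/15 has probability about 0.009. This is fair: 40% is a bound, and the table is the better guide to likelihood, subject to its assumed rates.

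Third, a failing VR arm need not go unnoticed. The target of 15 completers per arm would expose uneven loss, and usability, presence and cybersickness are measured. The protocol also states no progression rule, so nothing in it says that meeting the benchmarks launches a larger trial. These points soften the consequence but leave the criterion itself unchanged.

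Fourth, a hard per-arm rule at 15 per arm would often fail a sound trial. The calculation supports this, and no such rule is asked for.

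A reader might also infer from section 13.2 that people who withdraw their data disappear from the denominator, so that retention rises because they left. For example, 18/30 = 60% would become 18/25 = 72% if five of the twelve leavers were removed. The documents do not support that reading. Section 13.2 concerns data, not the count of those enrolled. Section 16.3 has enrolment tracked weekly, with consent documented for audit. The denominator is undefined; it is not defined wrongly.

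**Conclusion.** The point holds as a weakness in the primary criterion that is cheap to repair. As written, the retention and weekly-report benchmarks can be met with VR as low as 40%. For assumed true VR retention of 50% to 60% with TMH at 80% to 90%, the overall retention benchmark is met with probability 0.59 to 0.82, and is met while observed VR retention is below 70% with probability 0.38 to 0.60. These probabilities rest on 15 randomised per arm, independent participants, and retention rates that the protocol does not give. The 40% bound needs only the plain pooled reading and, for weekly reports, equal numbers of scheduled forms per arm.

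Separately, the enrolment figures in 5.0, 11.1 and 16.1 do not agree, so the base of the 70% is unclear. The enrolment benchmark is properly trial-level and is not criticised for lacking an arm.

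**What to change.** In section 16.1, and to match in 5.0:

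- Keep the overall 70%, 70% and 80% benchmarks.
- Add that retention, weekly-report completion and fidelity will also be evaluated and reported in each arm, with 95% confidence intervals and the between-arm difference.
- State that feasibility will not be concluded from the pooled figure alone when the VR figure is clearly below the benchmark.
- Define the retention denominator as all randomised participants, and the weekly-report denominator as all scheduled weekly assessments of randomised participants. Count any withdrawal as not retained; where data are withdrawn, keep only an anonymous count.
- Keep enrolment trial-level, and reconcile 30 enrolled, up to 60 enrolled, 3 per month and 30 completers across 5.0, 11.1 and 16.1.

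This takes a few sentences and no new data. The cost is imprecision: arm-level estimates on about 15 participants have wide intervals (11/15: 45% to 92%), so they should inform the judgement and not act as a hard pass mark.

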17.0 Provisions to Monitor the Data to Ensure the Safety of Subjects

17.1 Some questions asked during assessments and exposure exercises may cause participants distress, but this distress is expected to be similar to what participants would experience with routine care for specific fears/Phobias. The study therapist (i.e., Postdoctoral Fellow) will ensure that any questions causing distress are discussed with participants and will provide them with techniques to reduce distress. A temporary increase in the severity of anxiety is expected at the beginning of exposure therapy, along with a gradual decline in severity over the course of treatment. If participants are distressed and unable to participate in the study following baseline assessments, or at the end of the study participants feel that they are in need of further treatment, the study therapist (i.e., Postdoctoral Fellow) will provide a referral to therapist(s) in the participants local area. This will be provided verbally to participants and the study therapist (i.e., Postdoctoral Fellow) will follow up in one week via telephone to inquire as to the state of the referral and provide further assistance as necessary.

17.2 N/A

18.0 Provisions to Protect the Privacy Interests of Subjects

18.1 The research will be conducted via telephone, online, video conferencing, and virtual reality by IRB approved study staff located in a closed private clinic office in the University of South Florida Department of Psychiatry and Behavioral Neurosciences.

18.2 Study participants will provide informed consent. We will not access any previously existing records.

19.0 Compensation for Research-Related Injury

19.1 N/A

20.0 Subject Costs and Compensation

20.1 Patients who participate in this study will have internet and smartphone access, so we anticipate that they will have data and text message plans that will allow them to participate without any additional costs. However, there is the small risk that some participants may exceed their monthly data or text message limits during this study resulting in additional costs, for which they will be responsible. This risk will be discussed during the informed consent process.

20.2 If you will provide compensation to subjects, select all that apply:

 No Compensation	 Tokens (pens, food items, etc.)
 Financial Compensation (cash, gift cards)	 Other
 Course Credit (i.e. extra credit, SONA points)	

Participants will receive a \$50 eGift card for completing the baseline assessment, \$50 eGift card for completing the 6th therapy session, and a \$50 e-gift card for completing the 3-month follow-up assessment. There will be no partial compensation for partially completing either assessment.

21.0 Consent Process

21.1

 Obtaining Signed Consent (Subject or Legally Authorized Representative)	 Obtaining Consent Online (Waiver of Written Documentation of Consent)
 Obtaining Signed Parental Permission	 Obtaining Verbal Consent (Waiver of Written Documentation of Consent)
 Obtaining Signed Assent for Children or Adults Unable to Consent	 Waiving Consent and/or Parental Permission (Waiver of Consent Process)
 Obtaining Verbal Assent for Children or Adults Unable to Consent	 Waiving Assent/Assent is Not Appropriate
 Obtaining eConsent Signatures (Subject or Legally Authorized Representative)	 Obtaining eConsent Parental Permission
 Obtaining eConsent Assent for Children	

21.2 N/A

21.3 Study staff will obtain verbal consent from participants during the ≤60-minute videoconference-based consent and baseline assessment visit. We are requesting a waiver of written documentation of consent because any subjects face challenges with using a cursor and some encounter difficulties when typing their names. Participants will be sent a copy of the consent form, which will be screenshared for participants while it is being explained by the study therapist. The study therapist will ensure that participants understand all aspects of the study and consent form, and adequate time will be provided for questions relating to treatment, use of VR, audio recording sessions, and assessments. We will use an Informed Consent Checklist to document this process (see Informed Consent Checklist in Local Site Documents). The study therapist will obtain informed consent as the Conflict of Interest management plan prevents the PI and the coordinator ([name]) from conducting consenting activities.

